#### 9.1.3. During hospital stay (Day 1 (from time of randomisation) until discharge from hospital)

The following data will be collected **daily** from the time of randomisation, in line with the routine collection of usual care data:

- Current medication (concomitant medication; analgesic medication; other medication/treatments)
- Lung function assessments.
- FEV1 and FVC to be collected twice per day
- Rating of pain (VAS) every 4 hours on day 1-5, then on day 14 and at discharge
- Body temperature
- SOFA
- CPIS Day 5 only
- CXR interpretations
- Tracheal secretion
- Oxygenation
- Rating of pain (VAS) every 4 hours on day 1-5, then on day 14 and at discharge
- Critical care minimal data set
- Intervention insertion date/time (only recorded on the date of insertion)
- Intervention removal date/time (only recorded on the date of removal)
- Failure of intervention (i.e. SAP Catheter could not be inserted or removed within 24 hours)
- Routine laboratory tests: (WBC, CRP, culture of tracheal aspirate)
- ICU and/or hospital admission status
- Organ dysfunction through use of the SOFA score
- Other medications or treatments required for MRF
- Adverse events
- Survival status
- Blood samples (see section 9.1.5)

#### 9.1.4. After discharged from hospital (Month 1 and 3 from time of randomisation)

The following will be collected by the site research team after the participant has been discharged from the hospital:

- EQ-5D-5L
- Resource usage
- MRC dyspnoea scale at 3 months only
- BPI
- SF-MPQ-2
- Charleson Comorbidity Index
- Adverse events
- Survival status

These data can be obtained from the hospital's data management systems or via telephone interview with the participant.

#### 9.1.5.Blood sampling for future research

In anticipation of future studies, blood will be collected and spun from participants who have provided consent (either for themselves or where consent/ an opinion has been sought from a legal representative or consultee). These samples will be taken within 24 hours of randomisation, day 5 ( $\pm$  24h) and day 14 ( $\pm$ 24h) if the participant is still admitted and at discharge. The blood sample should be stored at -80°C, and eventually shipped in batches to the laboratory at the University of Birmingham. Full instruction of sample preparation and shipment will be available in a separate Work Instruction.

	Screening	Baseline	Days during hospital			ital	At discharge	Months post- Randomisation	
Visit	-	Day 0	1-5	6-13	14	15+	-	1	3
Time window	$\leq$ 72 hours	$\leq$ 48 hours		Dail	у		± 6 hours from discharge	± 7 d	ays
Eligibility check	х								
Valid informed consent		х							
Relevant medical history		х							
Basic demographic data		х							
Charleson Comorbidity Index		х						Х	х
Current medication		х	х	х	х	х	Х	Х	х
Date & time of injury		х							
Covid-19 diagnosis and treatment		х							
ICU/Ward admission details		х	x	х	x	x	x		
Randomisation		х							
Intervention insertion			х						
Intervention removal			х	х	х	х			
Failure of Intervention		х							
Date of discharge							Х		
Routine physical exam:									
Pregnancy test		х							
Body temperature		х	х	х	х	х			
AIS		х							
Frailty score		х							
SOFA		х	х	х	х	х			
CPIS		х	х	х	х	х			

#### Table 1: ERASER Trial Schedule of Assessment

	Screening	Baseline	Days during hospital			ital	At discharge	Months post- Randomisation	
Visit	-	Day 0	1-5	6-13	14	15+	-	1	3
Time window	$\leq$ 72 hours	$\leq$ 48 hours		Dail	у		± 6 hours from discharge	± 7 d	ays
Mechanism of injury		Х							
Other injury details		Х							
Lung function tests (FEV1, FVC twice per day )		х	х	х	x	х			
CXR interpretation (if any)		х	х	х	х	х			
Tracheal secretion		х	х	х	х	х			
Lung function assessments		х	х	х	х	х			
Oxygenation		х	х	х	х	х			
Pain rating (VAS at every 4 hours)		х	х		x		x		
Critical care minimal data set			х	х	х	х			
Routine bloods (CRP, WBC, Bacteria culture)		х	х	х	x	х			
Analgesic medication		х	х	х	х	х	Х		
Concomitant medication		х	х	х	х	х	Х		
Adverse events			х	х	х	х	Х	Х	Х
Survival status			х	х	х	х		Х	Х
Patient reported outcome measures (PROMs) – Interview administered									
Resource usage								Х	Х
EQ-5D-5L		х						Х	х
MRC dyspnoea scale									х
SF-MPQ-2								Х	Х
BPI								Х	х
Blood samples for future studies:		х	х		x		х		

# 9.2. PARTICIPANT WITHDRAWAL

Informed consent is defined as the process of learning the key facts about a clinical trial before deciding whether or not to participate. It is a continuous and dynamic process and the participants/consultee/legal representatives should be asked about their ongoing willingness to continue participation at all visits.

Participant/consultee/legal representative should be aware from the beginning that the participant can freely withdraw (discontinue participation) from the trial (or part of) at any time.

Participants who subsequently become ineligible following randomisation should be followed up according to all trial processes and will still have their data analysed, unless the participant/consultee/legal representative explicitly change the level of participation.

#### 9.2.1.Level of participation

The changes in levels of participation within the trial are categorised in the following ways:

**No trial intervention:** The participant would no longer like to receive the trial intervention, but is willing to be followed up in accordance with the schedule of assessments and if applicable using any central UK NHS bodies for long-term outcomes (i.e., the participant has agreed that data can be collected and used in the trial analysis).

**No trial related follow-up:** The participant no longer wishes to attend trial visits in accordance with the schedule of assessments but is willing to be followed up at standard clinic visits and if applicable using any central UK NHS bodies for long-term outcomes (i.e., the patient has agreed that data can be collected at standard clinic visits and used in the trial analysis, including data collected as part of long-term outcomes).

**No further data collection:** The participant no longer wishes to be followed up in any way for the purposes of the trial AND does not wish for any further data to be collected (i.e., only data collected prior to any changes of levels in participation can be used in the trial analysis).

## 9.2.2. Withdrawal documentation

The change of level in participation within trial (date, reason, and category of status change) should be clearly documented in the source documents and on the Change of Status CRF. Participant/consultee/legal representative can change the level of participation without giving a reason, although a reason would be useful in the pilot to help assess whether it is related to the design of the trial.

# 10. ADVERSE EVENT REPORTING

## 10.1. DEFINITION

The recording and reporting of Adverse Events (AEs) will be in accordance with the the Principles of Good Clinical Practice (GCP) as defined by the UK Policy Framework for Health and Social Care (2017) and the requirements of the Health Research Authority (HRA).

Definitions of different types of AEs are listed in table 2.

It is routine practice to record AEs in the participant's medical notes and it is also recommended that this includes the documentation of the assessment of severity, seriousness and causality (relatedness) with reference to the ERASER Protocol.

Type of events	Acronym	Definition				
Adverse Event	AE	Any untoward medical occurrence in a participant participating in the trial which does not necessarily have a causal relationship with the intervention received.				
Related Event	RE	An event which resulted from the administration of any of the research procedures.				
Serious Adverse Event	SAE	
 
An untoward occurrence that:
 
Results in death
 
Is life-threatening
 
Requires hospitalisation or prolongation of existing hospitalisation
 
Results in persistent or significant disability or incapacity
 
Consists of a congenital anomaly/ birth defect
 
Or is otherwise considered medically significant by the Investigator
 
				
Unexpected Event	UE	The type of event that is not listed in the protocol as an expected occurrence.				
Related and Unexpected Serious Adverse Event	N/A	A SAE that meets both the definition of a Related and Unexpected Event.				

**Table 2:** Types of Adverse Events and Definitions

# 10.2. AE/SAE REPORTING PERIOD

The reporting period for AEs and Serious Adverse Events (SAEs) in the trial will be from the day that the trial intervention was started until the end of the trial follow up period.

<sup>5 The term life-threatening is defined as diseases or conditions where the likelihood of death is high unless the course of the disease is interrupted.

<sup>6 Medical events that may not be immediately life-threatening or result in death or hospitalisation but may jeopardise the patient or may require intervention to prevent one of the other outcomes listed in the above definitions.

## 10.3. ADVERSE EVENTS IN ERASER

Participants that meet the eligibility criteria for the ERASER Trial will likely have suffered significant trauma and as a result may experience numerous AEs. As these events are well characterised, it is highly unlikely that these AEs will reveal any new safety information relating to the trial intervention, SAP. Due to this, events that meet the definition of an AE but not an SAE (see table 2) will not be required to be reported to the trial team, these AEs should however be recorded as per local practice.

## 10.4. SERIOUS ADVERSE EVENTS IN ERASER

It is recognised that the frequency of SAEs in this participant population may be high. Many of these SAEs will be anticipated due to the potential severity of the trauma experienced by the participant. We have therefore outlined anticipated SAEs that do not require reporting and anticipated SAEs that do not require expedited reporting. For all SAEs, the PI or delegate must do one of the following:

- **Record safety reporting-exempt SAEs** in the medical notes but not report them to the Trial Office on an SAE form as per Table 3.
- **Report SAEs in a non-expedited manner** to the Trial Office for the pre-defined subset of SAEs as per Table 4.
- **Report SAEs in an expedited manner** (within 24 hours of the site research team becoming aware of the event) to the Trial Office for SAEs not covered by the above 2 categories as per Table 5.

**Note:** when an SAE occurs at the same hospital at which the participant is receiving the trial intervention or is being followed up for trial purposes, processes must be in place to make the site research team aware of any SAEs, regardless of which department first becomes aware of the event, in an expedited manner.

#### 10.4.1. SAEs not requiring reporting

Several events that meet the definition of an SAE will not require reporting on the trials dedicated SAE form. If any of the events outlined below in table 3 occur during an individual's participation, from the date that trial intervention started through to end of follow-up, reporting the event on a SAE form is not required as the SAE is not considered to be critical to evaluations of the safety of the trial.

Expected SAE	Process
Pre-planned hospitalisation	Document in medical notes only
SAEs relating to a pre-existing medical condition or those that have occurred as a result of the participants injuries which are unrelated to MRF	Document in medical notes only

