#### 6.3. BLINDING

ERASER is an open label trial and is not blinded at the patient or investigator level. However, the trial will utilise a blinded end-point review committee (BERC) to assess the primary outcome to determine the rate of pneumonia 5 days after randomisation using CPIS and all available trial related clinical information.

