#### 8.2.2.Secondary Outcomes

The secondary outcomes for the ERASER trial are as follows:

- 1. Reduces pain
  - Numerical rating scale (0-10), recorded average every 4 hours on days 1 to 5, day 14 and before discharge.
  - Patient reported brief pain index (BPI) at 1 and 3 months post randomisation.
- 2. Improves ventilatory function
  - Incentive spirometry peak expiratory flow twice a day
- 3. Reduces the number of days ventilated and the requirement for invasive/non-invasive methods
  - Number of days ventilated
  - Type of ventilation invasive/non-invasive
- 4. Improves mortality
  - Mortality measured at 1 and 3 months post randomisation
- 5. Is safe and doesn't have unforseen Complications
  - Measured by SAEs review from randomisation until discharge
- 6. Impacts opiate consumption such as morphine and related compounds
  - Participant opiate consumption measured at discharge and 3 months post randomisation
- 7. Reduces length of hospital stay
  - Length of stay in hospital
  - Length of stay in critical care level two/three facility
- 8. Reduces hospital re-admission within 30 days of discharge
  - Measured by any hospital re-admission within 30 days of discharge

<sup>4 The blinded end point review committee will make their diagnosis based CPIS data and all available trial related clinical information

- 9. Impacts Patient-Reported Outcome Measures:
  - $\circ~$  EQ-5D-5L at 1 and 3 months post randomisation.
  - MRC dyspnoea scale at 3 months post randomisation.
  - o BPI at 1 and 3 months post randomisation.
  - SF-MPQ-2 at 1 and 3 months post randomisation

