#### 10.4.2. SAEs requiring non-expedited reporting

Where the safety profile is well established, the causal relationship between the intervention (or the participant's underlying condition), and the SAE, may be known. That is, such events are protocol-defined as "expected".

Such events should still be recorded by the site research team in the participant's medical notes and reported to the ERASER Trial Office, but it does not require expedited reporting (immediately on the site becoming aware of the event) since the assessment of expectedness for the specified events has been pre-defined. These SAEs can be reported alongside follow up CRFs at 1 or 3 months post randomisation. These expected SAEs are listed in Table 4 below.

Expected SAE ID	Expected SAE	Process
01	Hospital admissions lasting less than 24 hours	
02	Death - The cause of which is unrelated to intervention	
03	Organ failure – as indicated by SOFA score	
04	Infection to insertion site	Report on SAE Form and
05	Sepsis	provide to the ERASER Trial Office along with follow-up
06	Septic shock	CRFs.
07	Failure of extubation attempt	
08	New clinical diagnosis of pneumonia	
09	Primary cardiac bradyarrythmias and tachyarrythmias	

Table 4: ERASER Trial SAEs requiring non-expedited reporting

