#### 10.4.3. SAEs requiring expedited reporting

All SAEs not listed in section 10.4.1 and 10.4.2 must be reported to the ERASER Trial Office on a trial specific SAE Form within 24 hours of the site research team becoming aware of the event. Examples of SAEs that would require expedited reporting can be found in the table 5 below.

Please note: This list is **not** exhaustive.

**Table 5:** Examples of ERASER Trial SAEs that require expedited reporting

Expected SAE	Process
Anaesthetic toxicity	
Primary cardiac bradyarrythmias and tachyarrythmias where local investigators believe the cause local anaesthetic	Report on SAE Form and provide to the ERASER Trial Office within 24 hours of becoming aware of the event.

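### Tables 3 and 4 give opposite SAE-form instructions for the same event; an unblinded site's view of cause decides, leaving the SAE comparison open to inconsistent and possibly differential under-reporting

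*Protocol*

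**What the plan says.** Protocol section 10.4 sets up three routes for a serious event and leaves the choice to the site: "For all SAEs, the PI or delegate must do one of the following". The first route is for sites to record exempt events "in the medical notes but not report them to the Trial Office on an SAE form as per Table 3".

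Table 3 (section 10.4.1) has two entries. One is planned admission. The other is "SAEs relating to a pre-existing medical condition or those that have occurred as a result of the participants injuries which are" unrelated to the multiple rib fractures (MRF). The second entry is defined by cause and names no event type.

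Table 4 (section 10.4.2) requires a form, on a slower timetable, for nine listed events: short admissions, death, organ failure, insertion-site infection, sepsis, septic shock, failed extubation, new pneumonia and primary cardiac arrhythmias. These are defined by type, for example "Organ failure – as indicated by SOFA score". Only death carries a cause qualifier, and it concerns the intervention rather than other injuries: "Death - The cause of which is unrelated to intervention".

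Section 10.4.3 covers the remainder: "All SAEs not listed in section 10.4.1 and 10.4.2 must be reported to the ERASER Trial Office", within 24 hours.

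On use and blinding, secondary outcome 5 (section 8.2.2) is "Measured by SAEs review from randomisation until discharge", and section 6.3 says "ERASER is an open label trial and is not blinded at the patient or investigator level". Section 10.5.1 has the Trial Office send SAE data to the DMC.

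**The concern.** One table sorts events by cause and the other by type, so a single event can fall under both, with opposite instructions. In practice the site's opinion of cause then decides whether the event is collected at all. It should be a field recorded on an event already collected. That opinion is formed with knowledge of the allocation.

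At stake is the safety evidence. Section 10.3 keeps non-serious events away from the trial team, so SAE forms carry much of what the DMC and outcome 5 rely on. If sites resolve the overlap differently, counts vary between sites for reasons unrelated to patients. If they resolve it differently by arm, the comparison shifts even when there is no true difference.

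**Working it through.** The protocol gives no SAE rate and no split by cause, so there is no planned figure to reproduce. The check is of the text, followed by an illustration on assumed inputs.

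**1. Two test events against the tables.**

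| Event | Table 3 (by cause) | Table 4 (by type) |
|---|---|---|
| Sepsis from a wound other than the chest injury | Notes only | SAE form |
| Arrhythmia in a patient with known heart disease | Notes only | SAE form |

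The arrhythmia has a third possible route. If the local investigator believes local anaesthetic caused it, Table 5 (section 10.4.3) requires a form within 24 hours. The same rhythm can therefore go to the notes, to a slow form or to an expedited form, depending on the cause assigned.

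**2. Is there a precedence rule?** Section 10.4 says one of the three routes must be taken but does not rank the first two. Section 10.4.3 takes only what is in neither table. Sections 10.4.1 and 10.4.2 do not refer to each other's lists. No rule is stated.

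**3. Is the choice checked?** Under section 10.4.5, the chief investigator's causality review begins when the Trial Office receives a form. An exempted event never enters that review, although section 10.4.8 says the chief investigator reviews all SAEs.

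**4. Which Table 4 events are captured by a route that bypasses Table 3?**
- Deaths: survival status (sections 9.1.3 and 9.1.4), the Change of Status form (Table 9) and the mortality outcome.
- Organ dysfunction: daily SOFA in hospital (section 9.1.3).
- Pneumonia: the blinded committee reviews every participant (section 16.7).
- Failed extubation: only indirectly, through ventilation days and type (outcome 3).
- Short admissions: in part, through re-admission within 30 days of discharge (outcome 8).
- Sepsis, septic shock and arrhythmias: no separate outcome capture is stated.

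**5. What differential exemption would do (assumed inputs).** Let p be the true SAE rate, equal in both arms; f the share of SAEs that a site could attribute to pre-existing disease or a non-MRF injury; and e the probability that the site exempts such an event. The reported rate is p(1 − f·e), so p cancels:

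ratio (SAP/control) = (1 − f·e_SAP) / (1 − f·e_control)

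| e control | e SAP | f = 0.3 | f = 0.5 |
|---|---|---|---|
| 0.5 | 0.5 | 0.85/0.85 = 1.00 | 0.75/0.75 = 1.00 |
| 0.6 | 0.4 | 0.88/0.82 = 1.07 | 0.80/0.70 = 1.14 |
| 0.7 | 0.3 | 0.91/0.79 = 1.15 | 0.85/0.65 = 1.31 |

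Swapping the arms inverts the ratios: 0.93 and 0.88 for the milder gap, 0.87 and 0.76 for the wider one. With equal exemption the ratio is undisturbed, but 15% (f = 0.3) or 25% (f = 0.5) of SAEs go unreported in each arm.

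**The case against.** The strongest reply is that Table 4 can be read as prevailing. Section 10.4 describes it as a pre-defined subset, and section 10.4.2 says events explained by the participant's underlying condition are still to be reported. That reading is reasonable but not stated. Section 10.4.1 is equally unconditional in the other direction, so a site following either table can claim compliance.

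The second reply is that exemption is a deliberate economy in a trial assessed as low risk, in patients expected to have many serious events. That stands as a reason for having Table 3. It does not explain why Table 3 should remove events that Table 4 asks for by name.

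The third reply limits the reach, and it stands. Table 3 governs the SAE form only. Step 4 shows that deaths, SOFA scores and pneumonia arrive by other routes, and daily temperature, white cell count and CRP give some indirect information on sepsis. Section 10.4.1 also requires all serious events to be in the notes with causality and severity, and sections 12.2.1 and 12.2.2 allow source documents to be seen. Exempted events could therefore be retrieved, at the cost of returning to site records. A reader might infer that they are lost for good; the documents do not support that.

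A reader might also infer that only SAP patients have an anaesthetic explanation for an event, so exemption must run higher in controls. This goes too far. Table 3 turns on pre-existing disease or other injury, not on relation to the block. Section 14.2 also allows epidural or paravertebral analgesia in the control arm, so such an explanation is less available there, not absent.

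**Conclusion.** The overlap is in the text, no precedence rule resolves it, and the deciding judgement is unblinded and not centrally checked once an event is exempted. The SAE data behind outcome 5 and the DMC reports are therefore open to inconsistent and possibly differential under-reporting. The exposure is greatest for sepsis, septic shock and arrhythmias, and for short admissions that the re-admission outcome misses.

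It would be tempting to conclude that the SAE comparison is biased. The protocol does not show that. Relative bias under no true difference needs exemption rates that differ by arm, which the rule permits but nothing in the document demonstrates. Neither size nor direction can be derived; the ratios of 1.07 to 1.31, and their inverses, rest wholly on the assumed f and e. They apply to event counts. For patients with any SAE the shift could be smaller, since a patient with several events may still be counted after one is exempted. No false-positive rate is offered, because the protocol names no pooled SAE test to which it would apply.

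The change is worth making because it removes a contradictory collection rule cheaply, and because an analysis plan cannot by itself restore events that never reached a form.

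**What to change.** Reconcile the tables in two places.

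- **Section 10.4.1:** state that Table 3 does not apply to any event type listed in Table 4. Those events go on an SAE form in both arms whatever cause the site assigns, and the cause is recorded on the form. Table 3 then covers planned admissions and other SAE types only.
- **Section 8.2.2, outcome 5:** state that all reported SAEs are compared between arms irrespective of attributed cause. Keep expedited events such as anaesthetic toxicity in the comparison. Report insertion-site infection descriptively for the SAP arm, since it is tied to having a catheter. Outcome 5 should not be restricted to Table 4 types, because that would drop anaesthetic toxicity.

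The cost is two wording changes and some additional non-expedited forms at sites, mainly for events now left in the notes. No new assessment is needed; survival status and SOFA are already collected and can serve as a cross-check on deaths and organ failure. A limit remains: SAE types outside Table 4 would still be exempted by attributed cause.
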